Dendrite	Dendrite clinical systems, electronic research database
Section 251	The purpose of section 251 support is to give the data controller a legal means of providing access to confidential patient information without consent.
SOP	Standard Operating Procedure
SPSS	Statistical Product and Service Solutions (statistical software suite)
UHP	University Hospitals Plymouth NHS Trust
USS	UltraSound Scan
WBC	White Blood Cell

KEY WORDS:

Pulmonary embolism, Thrombectomy.

STUDY SUMMARY

Study Title TiPE

Study Design Prospective observational study to evaluate the use of Computer aided

vacuum thrombectomy (CAVT) within the context of intermediate and

high-risk PE.

Study Participants Patients presenting with intermediate or high-risk PE (as defined by

European Society of Cardiology (ESC) guidelines1) at one of the

participating hospitals.

Eligibility Criteria Study Site Criteria:

1. Availability of 16Fr Penumbra Flash

2. Operational PE Response team

3. Operator experience treating a minimum of 2 previous PE's and experience with Penumbra indigo systems (defined as 3 cases).

Inclusion Criteria Participants:

1. Clinical signs and symptoms consistent with acute PE with duration of 14 days or less

2. Patients who present with CT confirmed PE

3. Defined as intermediate or high-risk PE (according to ESC guidelines¹)

4. Date of CT imaging from within the two-year period

5. Patient is ≥ 18 years of age

6. Informed consent obtained

7. Evidence of cardiac dysfunction (Either biochemical or imaging features of RHS)

Exclusion Criteria:

- 1. Known serious, uncontrolled sensitivity to radiographic agents
- 2. CT not available to evaluate PE
- 3. Low Risk PE as defined by ESC guidelines¹
- 4. Current participation in another investigational drug or device study that may confound the results of this study. Studies requiring extended follow-up for products that were investigational but have since become commercially available are not considered investigational studies
- 5. Other medical, social, or psychological conditions that, in the opinion of the Investigator, precludes the patient from appropriate consent, could limit the patient's ability to participate in the study, including compliance with follow-up requirements, or that could impact the scientific integrity of the study

Planned Sample Size 2000 eligible patients and 200 thrombectomy patients

Follow-up Duration 6 months from date of PE or date of death, whichever is sooner

Planned Study Period 30 months

Primary Objective

- 1. To evaluate the effectiveness of PE CAVT as a treatment for intermediate and high-risk PE as measured by change pulmonary arterial pressure and in RV/LV (Right Ventricle to Left Ventricle diameter) ratio at 48 (+ 48 /- 24) hours post procedure.
- 2. Ascertain the mortality and morbidity profile for CAVT within intermediate and high-risk PE, within 48 (± 12) hours post procedure, 30 (± 7) days, 90 (± 14) days and at 6months (+/- 30 days).

Secondary Objective

- 1. To identify factors that determine the decision to use thrombectomy within the PERT team
- 2. To evaluate the factors that predict outcome of CAVT
- 3. To evaluate the patient tolerance and experience in the form of Patient related outcome measures (PROMS) of CAVT
- To evaluate the effectiveness and risk profile of CAVT in highrisk patients, including effects of concurrent lytic therapy where given
- 5. To evaluate the effect of service design on PE CAVT rate and outcomes
- 6. To compare variability in provision of CAVT between hospitals and its effect on performance and outcomes.
- 7. To evaluate the relationship between severity and outcome in patients receiving CAVT
- 8. To determine imaging features that are associated with poor outcomes in patients undergoing CAVT
- 9. To determine the effectiveness of CAVT in relationship to the age of the thrombus
- 10. To evaluate the perceived dyspnoea at 30 days, 90 days and 6 months after CAVT, and also in comparison to the non-intervened group
- 11. To evaluate Quality of life as assessed by EQ-5D-5L and PEmb-QoL at 30 days, 90 days and 6 month, and also in comparison to the non-intervention group
- 12. Incidence of device related SAE(s)

- 13. Evaluate the impact of the length of procedure time and the operator decided end point of CAVT, including technical success and its effect on outcomes
- 14. To evaluate the time to CAVT and its effect on outcomes and resource utilisation.

STUDY FLOW CHART

Identification of cohort

All patients who had intermediate or high-risk PE within the two-year period.

Screening for eligibility

Inclusion criteria participants:

- Clinical signs and symptoms consistent with acute PE with duration of 14 days or less
- 2. Patients who present with CT confirmed PE
- Defined as intermediate or high-risk PE (as per ESC guidelines¹)
- 4. Date of CT imaging within the two-year period
- 5. Patient is ≥ 18 years of age
- 6. Informed consent obtained
- 7. Evidence of cardiac dysfunction (Either biochemical or imaging features of RHS)

Inclusion criteria Operator:

 Operator experience treating a minimum of 2 previous PE's and experience with Penumbra indigo systems (defined as 3 cases).

Screening for eligibility

Exclusion criteria:

- Known serious, uncontrolled sensitivity to radiographic agents
- 2. CT not available to evaluate PE
- 3. Low Risk PE as per ESC guidelines¹
- 4. Current participation in another investigational study that may confound
- 5. Other medical, social, or psychological conditions that, in the opinion of the Investigator, precludes the patient from appropriate consent, could limit the patient's ability to participate in the study.

Exclusion

Patient choice

Data collection

Data on patients regarding patient demographics, physiological parameters, PESI score, CT findings, clinical status, procedural information, day 1,3,5 observations, length of stay, readmission rates, further procedures and outcome at 30 days, 90 days and 6months.

Final cohort for analysis

Full cohort analysis will be performed on anonymised data set.

1 INTRODUCTION

1.1 LAY SUMMARY

Pulmonary embolism is a blood clot on the lung, which can cause death or significant reduced quality of life. Sucking the clot out with a special tube (catheter) is a relatively new procedure that can be performed but doesn't have the data required to properly support its use in some patients. We know this procedure works in patients who have no other options and would almost certainly die without intervention. We currently don't know how well this procedure is tolerated, how well it works and what its complications are in patients who are moderately to severely unwell. The National Institute of Clinical Excellence (NICE), an advisory body, suggests more data is required to support its use in patients who are sick or very sick. This registry aims to support this growing evidence base to workout if the treatment is effective and the associated risks that come with using it. We are collecting data about this procedure and other treatments patients get offered to better inform clinicians and researchers.

1.2 RATIONALE FOR CURRENT STUDY

Acute intermediate-risk pulmonary embolism (PE) and high-risk PE (1) can be life threatening. The incidence of PE is increasing (2), and patients who survive the acute presentation may experience significant morbidity including reduced exercise tolerance, and decreased quality of life (QoL) (3). Often patients are treated with anticoagulation to stop the clot getting worse and encourage the body to slowly break up the clot. However in more severe cases thrombolysis medication can be given to actively break up the clot. Catheter directed thrombolysis can be used to target the lytic medication into the pulmonary arteries and reduced the systemic effects. Percutaneous thrombectomy is a newer treatment option that aspirates the clot, providing a faster and potentially lytic free solution to sick patients. Pulmonary artery thrombectomy (PAT) is a treatment option that is variably utilised and has unclear evidence base (4,5,6,7). The penumbra device uses a computer modulated vacuum aspiration system to both fatigue, breakup and aspirate the clot. This has been shown to be safe and effective in small cohorts (8). CAVT can prevent acute hemodynamic decompensation, alleviate acute PE-related symptoms, accelerate right ventricular recovery, and improve quality of life as measured by patient-reported outcomes (PROs) (4,5). Despite existing literature addressing clinical outcomes with PE treatment, comprehensive data on PE-related morbidity, PROs and longer-term outcomes after mechanical thrombectomy are still lacking.

1.3 PARTICIPANT AND PUBLIC INVOLVEMENT

Several patients who suffered from significant PEs, either receiving thrombectomy or other treatments including catheter directed thrombolysis were asked to review the protocol who considered the study

worthwhile and the involvement not onerous on patients. Lay person representative will be further involved in ongoing meetings.

In order to assess participants' lived experience of receiving vacuum thrombectomy for PE, a qualitative sub-study is planned. This study will build upon the existing literature (9, 10), that suggests patients suffer adverse physical and psychological consequences of PE and its management. To our knowledge, there is no literature exploring patients' experience of PE thrombectomy procedures specifically, thus highlighting an important gap in the literature. The qualitative sub-study will therefore provide insight into the experience of CAVT as a therapeutic intervention, deliver insights into how the patient experience may be optimised by IR providers, and infer whether there are any subjective differences in short-term morbidity and psychological sequelae as result of undergoing CAVT. The qualitative sub study will be protocolised separately as the 'TiPE-views' study.

1.4 DIVERSITY AND INCLUSION

The study will involve 12 sites, including remote costal population and cities. The 12 sites will include centres in the Southwest, North England and Scotland. This will help with capturing a diverse national population along with patients from deprived areas. As this is a hospital study, all adult patients referred to the PERT team will be screened. The study will collect data from intermediate and high-risk patients who are affected by cancer and pregnant women who have an increased risk of clotting (11). Both populations were excluded from previous clinical trials, although the risk of radiation during pregnancy needs to be acknowledged.

2 STUDY OBJECTIVES

2.1 PRIMARY OBJECTIVES

- 1. To evaluate the effectiveness of PE CAVT as a treatment for intermediate and high-risk PE as measured by change pulmonary arterial pressure and in RV/LV (Right Ventricle to Left Ventricle diameter) ratio at 48 (- 24 / + 48) hours post procedure.
- 2. Ascertain the mortality and morbidity profile for CAVT within intermediate and high-risk PE, within 48 (± 12) hours post procedure, 30 (± 7) days, 90 (± 14) days and 6 months (+/- 30 days).

2.2 SECONDARY OBJECTIVES

- 1. To identify factors that determine the decision to use thrombectomy within the PERT team
- 2. To evaluate the factors that predict outcome of CAVT
- 3. To evaluate the patient tolerance and experience in the form of patient related outcome measures (PROMS) of CAVT

- 4. To evaluate the effectiveness and risk profile of CAVT in high-risk patients, including effects of concurrent lytic therapy where given
- 5. To evaluate the effect of service design on PE CAVT rate and outcomes
- 6. To compare variability in provision of CAVT between hospitals and its effect on performance and outcomes.
- 7. To evaluate the relationship between severity and outcome in patients receiving CAVT
- 8. To determine imaging features that are associated with poor outcomes in patients undergoing CAVT
- 9. To determine the effectiveness of CAVT in relationship to the age of the thrombus
- 10. To evaluate the perceived dyspnoea at 30 days and 6 months after CAVT, and also in comparison to the non-intervened group
- 11. To evaluate Quality of life as assessed by EQ-5D-5L and PEmb-QoL at 30, 90 days and 6 months for all participants.
- 12. Incidence of device related SAE(s)
- 13. Evaluate the impact of the length of procedure time and the operator decided end point of CAVT, including technical success and its effect on outcomes
- 14. To evaluate the time to CAVT and its effect on outcomes and resource utilisation.

2.2 OUTCOMES

Effectiveness of CAVT will be determined by the change in RV/LV ratio on Echocardiography and the reduction in direct invasive measurement of the Pulmonary artery pressure at the beginning and end of the procedure.

Technical success will be determined by the operator comparing pre and post imaging and pulmonary artery pressures. Morbidity and mortality will be expressed as percentage of the cohort. Imaging features, service design, PERT team decision and comorbidities effect on outcomes will be assessed via regression analysis.

The service design and effect on thrombectomy will be assess by service questionnaire at site set up describing the service design factors. Patient reported outcomes like quality of life and breathlessness will be assessed to determine improvement as per their validated questionnaires.

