6.2 ANALYSIS

Patient demographic and clinical characteristics will be summarised using appropriate descriptive statistics. The primary outcome, change in LV/RV ratio before and at 48 hours post baseline will be summarised according to risk group and overall and will be assessed with a two-sided paired t-Test. Linear regression analysis will be used to identify factors, including severity, affecting the change in LV/RV ratio. Survival analysis will be used to model factors affecting mortality. Data will be analysed using R or Stata. An unblinded interim analysis at 100 patients will be performed at 6 month follow up with focus on the primary outcomes. No Stop/Go criteria will be applied as the PE response team decision to treat or not is not protocolised and the study is observational only. A detailed statistical analysis plan will be written with the University of Plymouth Medical Statistics group and finalised before database lock.

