7.1 DATA FLOW DIAGRAM

7.2 DESCRIPTION OF THE DATA

Sample data points will include the following for **ALL** patients:

Patient demographics

Age, Sex, Medical History, Cancer, Pregnancy, Time of first symptoms, presenting hospital, admission from location (e.g. Own Home/nursing home) transfer in, previous PE, Anticoagulation, Concurrent DVT and Position.

Admission / Diagnosis (at point of diagnosis of PE if not on admission)

Admission observations, Biochemistry including Temperature, BP, Pulse, oxygen saturations and GCS, biochemistry including: WCC, RBC, CRP, GFR and BNP and Troponin

CT findings (including Evidence of RHS parameters including IVC contrast reflux, Septal flattening, clot location, reporter grade)

Base line (Day of referral to PERT if not day of admission)

PESI score, , RV/LV ratio CT, RV/LV ratio USS. Presence of right atrial clot, PFO presence on Echocardiography, eligibility for thrombolysis (e.g. recent head trauma/ ischaemic stroke, previous ICH, Intracranial neoplasm, GI malignancy, GI haemorrhage in previous 21 days, Recent surgery, BP >185, active bleeding, infective endocarditis, Clotting abnormalities), If Thrombolysis given, including dose.

PER Team first assessment including date and time

PER Team initial decision outcome, date and time

PER Team review - Change Decision, date and time - and change in observations and Biochemistry PER Team review - Change Decision 2, date and time - and change in observations and Biochemistry

Discharge

Further procedures, length of stay, (including ICU, HDU, Ward), mortality, Place of discharge to. IVC filter insertion.

Follow up

Day 30 (± 7 days): All cause and PE related Mortality, Local readmission – Patient questionnaire: PEmb-QoL, EQ-5D-5L, Borg Scale

Day 90 (± 14 days): Mortality, Local readmission – Patient questionnaire: PEmb-QoL, EQ-5D-5L, Borg Scale

6 months (+/- 30 days): All cause and PE related Mortality – Patient questionnaire: PEmb-QoL, EQ-5D-5L, Borg Scale

Those undergoing CAVT will have the following additional data collected:

Procedural success and outcome. Procedural time, Access route, Aspiration device used, Separator used, Heparin given, including dose, Concurrent Lysis used, including dose. Thrombectomy time. Pulmonary arterial pressure at start, Pulmonary Arterial pressure at finish. Requiring further procedures, Length of stay, IVC filter insertion, readmission along with:

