Day 1 – Observations, including Temperature, BP, Pulse, oxygen saturations and GCS, biochemistry including: WCC, RBC, CRP, GFR and BNP and Troponin (if available)

Day 2 (+ 2 days / - 1 days) – Observations, including Temperature, BP, Pulse, oxygen saturations and GCS (if available). Echocardiogram with LV/RV ratio

Day 3 – Observations, including Temperature, BP, Pulse, oxygen saturations and GCS, biochemistry including: WCC, RBC, CRP, GFR and BNP and Troponin (if available) Day 5 – Observations, including Temperature, BP, Pulse, oxygen saturations and GCS, biochemistry including: WCC, RBC, CRP, GFR and BNP and Troponin (if available)

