12 APPENDICIES

12.1 APPENDIX 1 – SCHEDULE OF EVENTS

For ALL Participants

Assessments	Visits						
	PERT referral	Discharge	30 (± 7) days post op	90 (± 14) days post op	6 (± 1) months post op		
Informed consent	X						
Demographics	Х						
Admission observations	Х						
Biochemistry (WBC, RBC, CRP, GFR, BNP)	X						
PESI score	X						
CT findings	Х						
RV/LV ratio	Х						
Pulmonary arterial pressure	Х						
PERT team assessment	Х						
Further procedures		X					
Length of stay		Х					
Mortality		X	Χ	Х	X		

	Visits					
Assessments	PERT referral	Discharge	30 (± 7) days post op	90 (± 14) days post op	6 (± 1) months post op	
Readmission			Х	X		
Questionnaires						
PEmb-QoL			Х	X	X	
ED-5D-5L			Х	X	X	
Borg Scale			Х	X	X	

Only for CAVT treatment

Accomments	Visits						
Assessments	PERT referral	Day 1 post op	Day 2 post op	Day 3 post op	Day 5 post op	Discharge	
Procedure outcome	X						
Thrombectomy time	Х						
Observations		Х	Х	Х	Х		
Temperature		Х	Х	Х	Х		
Blood Pressure		Х	Х	Х	X		
Pulse		Х	Х	Х	X		
Oxygen saturation		Х	Х	Х	Х		
Glasgow Coma Scale		Х	Х	Х	Х		
Biochemistry (WBC, RBC, CRP, GFR, BNP)		Х		Х	Х		
Echocardiogram with LV/RV ratio			Х				
Further procedures						Χ	
Length of Stay						Χ	
Mortality						X	
Readmission							
Questionnaires							
PEmb-QoL							

Accesaments	Visits					
Assessments	PERT referral	Day 1 post op	Day 2 post op	Day 3 post op	Day 5 post op	Discharge
ED-5D-5L						
Borg Scale						

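### The before-after RV/LV test in CAVT patients alone cannot separate a CAVT effect from background recovery or co-treatment, yet the protocol uses that change to determine effectiveness

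*Protocol*

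**What the plan says.** The first primary objective (Protocol, section 2.1) is: "To evaluate the effectiveness of PE CAVT as a treatment for intermediate and high-risk PE". It is measured by change in pulmonary arterial pressure and in RV/LV ratio at 48 hours, with a window of -24 to +48 hours, so 24 to 96 hours after the procedure.

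Section 2.2 (Outcomes) names two measures. The first is: "Effectiveness of CAVT will be determined by the change in RV/LV ratio on Echocardiography". The second is the reduction in "direct invasive measurement of the Pulmonary artery pressure at the beginning and end of the procedure".

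Section 6.2 names the RV/LV change as the primary outcome, to be summarised overall and by risk group; it "will be assessed with a two-sided paired t-Test". No comparator is planned for it. (The protocol writes both RV/LV and LV/RV; I take them to mean the same measure.)

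On data collection, section 7.2 lists baseline RV/LV by CT and ultrasound for all participants. The Day 2 item "Echocardiogram with LV/RV ratio" comes under the heading "Those undergoing CAVT will have the following additional data collected". Appendix 1 agrees: the Day 2 echo is in the table "Only for CAVT treatment", and the all-participant table has RV/LV at PERT referral only.

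On the course without CAVT, section 1.2 says: "Often patients are treated with anticoagulation to stop the clot getting worse and encourage the body to slowly break up the clot". It also credits CAVT with speeding up right ventricular recovery.

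**The concern.** A paired test takes zero change as its reference. That reference identifies a treatment effect only if the ratio would have stayed put without the treatment. The protocol's own rationale points the other way: anticoagulation allows gradual clot breakdown, and a treatment that speeds recovery presupposes some recovery to speed.

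Two other components enter the same difference. Concurrent lysis may be given (secondary objective 4; section 7.2). Entry also requires evidence of cardiac dysfunction (inclusion criterion 7), so patients selected partly on an abnormal ventricle may drift back towards their usual value on re-measurement.

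The study enrols patients who do not receive CAVT and records their baseline ratio. It plans comparisons with them for dyspnoea and, in the study summary, for quality of life. For RV/LV, however, no follow-up value is scheduled in them. The regression in section 6.2 on factors affecting RV/LV change cannot fill the gap, because planned change values exist only in treated patients. An analysis plan can choose a model but cannot analyse values that were never collected.

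At stake is whether a positive RV/LV result can be read as an effect of CAVT.

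**Working it through.** **Inputs.** From section 6.1: SD of change 0.27 and mean reduction 0.38 (from the earlier study used for sizing), n = 200 CAVT patients, alpha 0.05, target d = 0.2, stated power 90%. From section 6.2: paired t-test, two-sided. Assumed, because the protocol gives no figure: the mean background fall in RV/LV by 24 to 96 hours, taken from 0.02 to 0.10.

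**Step 1. The plan's own figures.**
- Effect size in the earlier study: 0.38 / 0.27 = 1.41, consistent with the stated d > 1.
- Power at n = 200 and d = 0.2: the noncentrality is 0.2 × √200 = 2.83, which gives 80.4% two-sided, not 90% (88.0% if one-sided). This is a separate matter and the present point does not depend on it.

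**Step 2. Smallest observed fall that is significant.**
- Standard error = 0.27 / √200 = 0.0191.
- Critical value t(0.975, 199) = 1.972.
- Threshold = 1.972 × 0.0191 = 0.038 RV/LV units, and 0.038 / 0.38 = 10% of the cited reduction.
- For comparison, d = 0.2 corresponds to 0.2 × 0.27 = 0.054 units.

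**Step 3. Chance of a significant test if CAVT adds nothing.** Let the whole mean change be a background fall m. The noncentrality is m / 0.0191, and the two-sided noncentral t distribution on 199 degrees of freedom gives:

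| Assumed background fall m | m / 0.27 | Noncentrality | Probability of significance |
|---|---|---|---|
| 0.02 | 0.074 | 1.05 | 18% |
| 0.04 | 0.148 | 2.10 | 55% |
| 0.05 | 0.185 | 2.62 | 74% |
| 0.054 | 0.200 | 2.83 | 80% |
| 0.10 | 0.370 | 5.24 | 99.9% |

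The 0.054 row is the effect the study is sized to detect: a background fall of that size is detected as readily as a CAVT effect of that size, because the test sees only their sum.

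**Step 4. The two measures side by side.** RV/LV is read before treatment and again 24 to 96 hours after the procedure, so days of background care lie between the readings. Pulmonary artery pressure is read at the start and end of the procedure. Neither has a control, but slow recovery over days can explain little of the second.

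**The case against.** The strongest reply is that this is openly an observational registry that does not alter the treatment pathway, and that a before-after RV/LV change is a legitimate description and matches the study used for sizing. That stands. The fault lies in letting this change determine effectiveness, not in measuring it.

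Several stronger readings are tempting, and the protocol does not support them:

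- *That effectiveness rests on RV/LV alone.* Pulmonary artery pressure is named in both the objective and the outcomes section, and it is much less open to recovery over days.
- *That a significant p-value will be declared as effectiveness.* Section 6.2 sets no such rule. It summarises the change as well as testing it, and it disclaims stop/go criteria. A mean fall near 0.04 would be visible as about a tenth of the cited 0.38.
- *That a small background fall would certainly produce a positive test.* At 0.04 it is close to a coin toss.
- *That every CAVT patient has background treatment.* Section 1.2 says anticoagulation is common, and section 7.2 records heparin and lysis where used. Section 1.2 also describes clot breakdown on anticoagulation as slow, which limits what can be assumed by 24 to 96 hours.
- *That about 1,800 controls are available.* That is 2,000 - 200 and assumes the 2,000 includes the CAVT patients.

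It is also fair to say that routine echoes in non-CAVT patients would be selective and confounded by the PERT decision. They would not supply the missing counterfactual. That is why collecting them is only an optional part of the remedy.

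**Conclusion.** The point holds for the RV/LV half of primary objective 1. The paired test estimates change after CAVT plus whatever else happened over 24 to 96 hours, and the planned data contain no follow-up RV/LV from which the rest could be estimated. Pulmonary artery pressure gives partial and less exposed support, but it too has no comparator and does not rescue attribution of the RV/LV change.

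The test is sensitive to small background shifts: significance begins at an observed fall of about 0.038, and with no CAVT effect the chance of significance runs from 18% at a background fall of 0.02 to 99.9% at 0.10. These figures assume that the SD of 0.27 carries over from a cohort that section 6.1 describes as having different treatment thresholds, that all 200 patients have paired values, and that background falls lie in the range shown. The size of the actual bias cannot be derived from the protocol.

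A reader might infer that the RV/LV result will be meaningless or that CAVT does not work. Neither follows. A fall near 0.38 would need a large background component to be explained away, and the protocol neither supplies nor rules out one.

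**What to change.** **(a) Wording, in sections 2.1, 2.2 (Outcomes) and 6.2.** State that the RV/LV paired analysis estimates the change after CAVT plus background treatment, that it will be reported as a mean change with a confidence interval, and that effectiveness attributable to CAVT will not be concluded from it alone. This costs a protocol text change and a more modest headline claim.

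**(b) Optional data item, in section 7.2 and the all-participant table of Appendix 1.** Record the RV/LV ratio from any routine echocardiogram at 24 to 96 hours, with date and time, if available. State the time origin for non-CAVT patients, who have no procedure. No echo is mandated. Report the baseline-adjusted change in non-CAVT patients beside the CAVT result as descriptive context only. This costs one extra field. Its limit is that these echoes will be incomplete, selected and confounded by indication, so they should not be presented as a control group.

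If (b) is declined, (a) alone still removes the unsupported attribution.

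### Technical success is graded by the treating operator without a common criterion, so objective 13 is partly confounded with operator grading; the recorded pressure change should be its main measure

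*Protocol*

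**What the plan says.** Protocol 2.2 Outcomes gives a rule for technical success: "Technical success will be determined by the operator comparing pre and post imaging and pulmonary artery pressures". The rule names who decides and the inputs. It gives no threshold, grading scale or second reader, and none appears elsewhere in the protocol.

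The label is used in objective 13 among the secondary objectives: "Evaluate the impact of the length of procedure time and the operator decided end point of CAVT, including technical success and its effect on outcomes". Secondary objective 6 concerns hospitals: "To compare variability in provision of CAVT between hospitals and its effect on performance and outcomes". It does not mention technical success.

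For patients undergoing CAVT, section 7.2 lists "Procedural success and outcome", without a definition and under a different term, and also "Pulmonary arterial pressure at start, Pulmonary Arterial pressure at finish". The schedule in Appendix 1 has only an undefined procedure outcome.

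Effectiveness is defined separately in 2.2 Outcomes: "Effectiveness of CAVT will be determined by the change in RV/LV ratio on Echocardiography and the reduction in direct invasive measurement". The invasive measurement is pulmonary artery pressure, taken when the procedure starts and when it ends.

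**The concern.** The protocol fixes who grades success but not what counts as success. Two patients with the same pressures and images can be classed differently because their operators hold different private standards. The operator also decides the procedural end point, and so grades a result at which they chose to stop. Objective 13 analyses both items, and they are not independent.

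Two things are at stake. A technical success rate pooled over 12 sites would have no fixed meaning. The association between technical success and outcome would mix the procedural result with the grader's standard.

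This goes beyond detail that can wait for the SAP. The label is created when each case is recorded. A later document can derive a new variable from the pressures, but it cannot standardise judgements already made.

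**Working it through.** **No plan figure to reproduce.** The protocol attaches no rate, sample size or power to technical success. The check is a comparison of sections, followed by an illustration.

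**Which objectives depend on the label**

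| Item | Depends on the operator's label? |
|---|---|
| Primary objective 1 (RV/LV ratio, pressure change) | No; both are measured |
| Primary objective 2 (mortality, morbidity) | No |
| Objective 13 | Yes; the label is named |
| Objective 6 | Only if performance is taken to include it |
| Questionnaire objectives | No |

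**Illustration 1: how much the spread of pass marks matters**

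From the protocol: 12 sites (1.4) and 200 CAVT patients (6.1). 200/12 = 16.7 per site, modelled as 8 sites of 17 and 4 of 16 (136 + 64 = 200).

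Assumed, because the documents give no figures: a normal pressure change in SD units, the same true distribution at every site, 85% success at the average pass mark, and one pass mark per site.

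- Average pass mark: c0 = Φ⁻¹(0.15) = −1.036.
- Site pass mark: c = c0 + τ·Z, with Z standard normal. Site success probability: p = 1 − Φ(c).
- Lowering or raising the pass mark by 0.5 SD: 1 − Φ(−1.536) = 94% and 1 − Φ(−0.536) = 70%, against 85%. Nothing about the patients has changed.
- Chi-square test across sites (11 df, 5% level), 4,000 simulated studies per row:

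| τ (SD of pass marks) | Significant site difference | Median range of true site success rates | Mean pressure change, success minus failure |
|---|---|---|---|
| 0 | 4.4% | 0 points | 1.83 SD |
| 0.25 | 22% | 18 points | 1.76 SD |
| 0.5 | 73% | 37 points | 1.59 SD |
| 1.0 | 99% | 69 points | 1.21 SD |

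At τ = 0 the last column agrees with φ(c0)/(0.85 × 0.15) = 1.83. It shows that the label keeps real information at every spread, but less as grading varies more.

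**Illustration 2: a percentage scale with wide pass marks**

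Assumed: mean pressure fall 20% or 25%, SD 15%. Success proportion = 1 − Φ((pass mark − mean)/SD).

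| Pass mark | Mean fall 20% | Mean fall 25% |
|---|---|---|
| >0% | 91% | 95% |
| 10% | 75% | 84% |
| 20% | 50% | 63% |
| 30% | 25% | 37% |

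With site pass marks uniform over 0–30% and 17 patients per site, the same test is falsely significant in about 97% (mean 20%) and 95% (mean 25%) of studies, against 4–5% with one common pass mark. This is a wide spread: its SD is 30/√12 = 8.7 percentage points, and 8.7/15 = 0.58 outcome SDs.

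Both illustrations point the same way, but the size is set by the assumed spread. Both also ignore the imaging part of the judgement.

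**The case against.** The strongest case on the other side has five parts.

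- **Scope.** A reader might infer that the study's site comparisons will measure operator leniency. The documents do not support that. Objective 6 does not name technical success, no between-site test of it is planned, and the chi-square test above is only a device for showing the mechanism. The stated plan is regression: "Imaging features, service design, PERT team decision and comorbidities effect on outcomes will be assessed via regression analysis". Comparisons on RV/LV ratio, pressure, mortality or questionnaires do not use the label. This stands.
- **The operator's role is intended.** Objective 13 sets out to study "the operator decided end point of CAVT, including technical success and its effect on outcomes", so operator judgement is partly its subject. This stands, but such a study still needs a measured procedural result beside the judgement.
- **The judgement is not free-form.** Its inputs are named, and section 3.2 sets a minimum of operator experience. This is true, but experience is not a shared pass mark.
- **Upward bias.** A reader might infer that the success rate will be too high. The documents hold no reference standard against which to show that.
- **A pressure-only definition loses information.** The protocol bases technical success on imaging as well as pressure. A pressure cut-off would drop the imaging and dichotomise a primary measure. This stands, and is a reason to keep the operator's label rather than replace it.

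**Conclusion.** The point holds in a limited form. Technical success is self-assessed with no common criterion, and its grader also decides the end point. Objective 13, and any site or operator comparison that uses the label, is therefore partly confounded with operator grading. The label is contaminated but not empty.

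The primary effectiveness results are not affected. Objective 6 is affected only if its term performance includes technical success.

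The size is unknown. False site differences in the illustrations run from 22% to 99% of studies, depending wholly on an assumed spread of pass marks, so no single figure should be quoted as an estimate for this study. This is a cheap improvement to a secondary objective, not a flaw that invalidates the study.

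**What to change.** In Protocol 2.2 Outcomes:

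1. Rename the item *operator-reported technical success*, and use the same term in section 7.2 and Appendix 1.
2. State that for objective 13, and for any between-site comparison of procedural result, the main measure is the continuous change in pulmonary artery pressure from start to finish, with the operator-reported label as a secondary descriptor.
3. State that any binary success rate reported as a study result will be derived centrally, by one criterion fixed in advance and applied identically at all sites.

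**Cost.** This is a change of wording; section 7.2 already collects both pressures. Patients missing a start or finish pressure drop out of the measured analysis, and their number should be reported. Pressure alone does not capture the imaging component, which is why the operator's label is kept. No treatment decision changes.
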